### **10.3 OTHER SECONDARY EFFICACY MEASURES**

#### ***10.3.1 6MWD at Other Visits Except Week 24***

The method for analysis of change in 6MWD at other visits up to Week 48 (except Week 24) is the same as for the analysis of 6MWD at Week 24, and it has been described in Section [10.2.1](#).

The observed values for 6MWD at all visits, including visits beyond Week 48, will be listed and descriptively summarized according to the requirements described in Section [8](#).

#### ***10.3.2 Borg Dyspnea Score***

The Borg dyspnea score is a 10-point scale rating the maximum level of dyspnea experienced during the 6MWT. Scores range from 0 (for the best condition) to 10 or more (for the worst condition). Scores will be listed with the corresponding 6MWT data for each subject. Change from Baseline for visits up to Week 48 will be compared between the 2 treatment groups using non-parametric Hodges-Lehmann estimator and Wilcoxon rank-sum test as well as parametric 2-sample t-test. Values for missing or excluded assessments up to Week 48 will be imputed. For those patients who withdrew early due to death, or a clinical worsening event without Borg dyspnea score measurement at visits up to Week 48, the Borg dyspnea score is set to worst score of 10; for all other withdrawals without Borg measurement, the LOCF method is used for imputation.

The observed values for Borg dyspnea score at all visits, including visits beyond Week 48, will be descriptively summarized according to the requirements described in Section 8.

### **10.3.3 WHO FC**

WHO FC values (ie, class I, II, III, or IV) will be listed for all subjects at each assessment time point. Class I, II, III, or IV will be assigned values 1, 2, 3, 4 for the calculations. The shift from Baseline in WHO FC (categorized as Improved, No Change, and Deteriorated) for visits up to Week 48 will be compared between the 2 treatment groups using Fisher's exact test. The change from Baseline in WHO FC for visits up to Week 48 will be compared between the 2 treatment groups using the non-parametric Hodges-Lehmann estimator and Wilcoxon rank-sum test. Values for missing or excluded assessments up to Week 48 will be imputed. For those patients who withdrew early due to death or a clinical worsening event without WHO FC measurement at visits up to Week 48, the WHO FC is set to the worst class value of IV; for all other withdrawals without WHO FC measurement, the LOCF method is used for imputation.

### **10.3.4 NT-proBNP**

NT-proBNP at weeks 12 and 36 will be analysed in the same way as described in Section 10.2.2. In addition, NT-proBNP at weeks 12, 24, and 36 will also be analysed with LOCF imputation for missing data. NT-proBNP at other timepoints will only be summarized.

### **10.3.5 Hemodynamic Parameters**

Values of all hemodynamic parameters obtained as part of the optional hemodynamic study (heart rate, systemic arterial pressure systolic [SAPs], systemic arterial pressure diastolic [SAPd], systemic arterial pressure mean [SAPm], pulmonary artery pressure systolic [PAPs], pulmonary artery pressure diastolic [PAPd], pulmonary artery pressure mean [PAPm], right atrial pressure mean [RAPm], pulmonary capillary wedge pressure mean [PCWPm], systemic arterial oxygen saturation [SaO2], mixed venous oxygen saturation [SvO2], CO Thermodilution, CO Fick, and BSA) will be listed for all subjects with hemodynamic measures. Additional hemodynamic parameters, including cardiac index, SVR, SVRI, PVR, and PVRI, will be derived according to the formulas described in Section 8.5.

The values and their respective changes from Baseline to Week 24 will be summarized by treatment group for each hemodynamic parameter. The difference between treatment groups for the change from Baseline to Week 24 will be tested using analysis of covariance, with change from Baseline as the dependent variable, treatment as the fixed effect, and Baseline measure as the covariate. The results from the non-parametric Wilcoxon rank-sum test will also be provided. The analyses will be based on the observed cases, and no imputation will be performed for the missing values.

## **10.4 EXPLORATORY ANALYSIS**

### ***10.4.1 The low risk-profile analysis***

Risk categories will be defined and the shift in risk categories will be analyzed according to the method defined in Weatherald et al (Weatherald 2018). The number and percentage of subjects with a low risk profile at Week 24 or other time points will be calculated and a treatment group comparison will be performed.

### ***10.4.2 Optional Evaluation of Biomarkers***

The optional evaluation of biomarkers will be specified in a separate document and not covered in this SAP.

### ***10.4.3 Optional Evaluation of Pharmacogenomics***

The optional evaluation of pharmacogenomics will be specified in a separate document and not covered in this SAP.

## **11 HEALTH OUTCOMES**

### **11.1 QUALITY OF LIFE MEASURES**

Quality of life was not assessed during this study.

### **11.2 RESOURCE UTILIZATION MEASURES**

All details for all hospitalizations will be listed. Number of hospitalizations, number of hospitalizations for PAH, total duration of hospitalization, and total duration of hospitalization for PAH will be summarized for each treatment group.

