3 EXPERIMENTAL PLAN

3.1 STUDY DESIGN

This is an international, multi-center, randomized, double-blind, placebo-controlled, event driven study in subjects with PAH. Subjects will be assessed during the Screening period to determine eligibility for the study, which will be confirmed during the Baseline visit prior to randomization. Once randomized, subjects will return for study visits every 4 weeks for the first 12 weeks, then every 12 weeks for the duration of the study. Subjects will continue in the study until either they experience clinical worsening as defined in the protocol, approximately 205 adjudicated events have occurred, or they prematurely discontinue participation in the study for any reason other than protocol-specific clinical worsening. If a subject meets the definition of clinical worsening during the study and receives only short term (28 days or less) treatment with an infused or inhaled PGI₂ therapy for worsening PAH, they will be permitted to enter the open-label extension study (TDE-PH-311). If a subject prematurely discontinues the study for any reason other than clinical worsening, or receives long-term (29 days or more) treatment with an infused or inhaled PGI₂ therapy for worsening PAH, they will not be permitted to enter the open-label extension study. Otherwise, all subjects actively participating in the study will be allowed to transition to the open-label extension study after approximately 205 adjudicated clinical worsening events have occurred.

At each scheduled visit, subjects will undergo the following efficacy assessments: clinical worsening, exercise capacity (6MWD and Borg dyspnea score), and WHO Functional Class. Plasma samples will also be collected for measurement of NT-proBNP at Baseline, Week 12

Week 24, Continued Visit 1 and at every other Continued Visit thereafter. See [Table 3-1](#) for the overall schedule of times and events.

Additionally, subjects may participate in an optional hemodynamic sub-study in which hemodynamic parameters will be assessed by RHC before randomization and following 24 weeks of treatment with study drug.

Safety will be assessed via vital signs, AEs, and clinical laboratory parameters. Subjects will also undergo a 12-lead ECG at Screening and Week 24. At every protocol-required visit, measures of exercise capacity will occur within 3 to 6 hours following administration of the last dose of study drug.

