9.1.3 Adverse Events Associated with Progression of PAH

Expected events that are related to the progression of a subject's PAH are defined in Appendix 15.6. All events that occur during the course of the study that are included on this list and felt to be related to the progression of the disease by the Investigator should not be recorded as AEs in the eCRF as these PAH symptoms will be evaluated and recorded as an efficacy endpoint and/or will be captured as disease related events.

However, an event must be recorded as an AE/SAE in the eCRF, if it meets one or more of the following criteria:

- There is a reasonable possibility that it may have been caused by study drug.
- It is serious.
- It has occurred at greater than expected severity (intensity, frequency, or duration).

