### ***10.1.1.3 Sensitivity and Subgroup Analyses***

The primary efficacy analysis of time to adjudicated clinical worsening events will also be provided for the Per-protocol Population.

The following sensitivity analyses will be performed:

- For all subjects who drop out from the study early, they are considered as having a clinical worsening event. Time to event will be calculated from randomization to subject's discontinuation date.
- For all subjects who drop out from the study early due to AEs, they are considered as having a clinical worsening event. Time to event is calculated from randomization to subject's study discontinuation date.

The time from randomization to clinical worsening will also be compared between treatment groups using a Cox proportional-hazards regression model, adjusting for Baseline 6MWD category ( $\leq 350$  meters versus  $> 350$  meters) and background PAH therapy (as a categorical variable: PDE5-I/sGC stimulator or ERA). Hazard ratio and its 95% confidence interval will be calculated. SAS Procedure PHREG will be used and the pseudo SAS statements are listed below:

```
proc phreg;
  Model TimeToWorsening*Censor_Status(1) = treatment;
  Strata BGTX B_6MWD / risklimits ties=efron;
run;
```

where BGTX variable denotes the background therapy and B\_6MWD denotes the Baseline 6MWD category  $\leq 350$  meters versus  $> 350$ .

Subgroup analyses will be performed on the following factors: background PAH therapy, PAH etiology, Baseline WHO FC, age group (<65 years versus  $\geq 65$  years), Baseline 6MWD category, sex (male versus female), maximum dose achieved (<9 mg versus  $\geq 9$ mg total daily dose), and geographic region as specified in Section 8.2. The estimated hazard ratio between the active and placebo groups from this model will be calculated and displayed along with its 95% confidence interval on the summary and analysis table and plot.

Since clinical worsening is a composite endpoint, the following components of this composite endpoint will also be summarized and analyzed with the same approach as the composite endpoint:

- Time to death (all causes) during the study
- Time to hospitalization due to worsening PAH

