### 12.2 ADVERSE EVENTS

All AEs will be coded using MedDRA and will be listed by treatment group, including all the details on the eCRF page plus an indicator of whether the event was treatment emergent. The AE listings will include the AE verbatim term and its corresponding PT and SOC.

The AE summary tables will be limited to include only treatment-emergent AEs and will be summarized for each treatment group. Treatment-emergent AEs are those AEs with an onset date equal to or after the start date of the study drug. The non-treatment emergent AEs (the AEs that occur after signing the informed consent form, but before receiving study drug, will be listed but will not be included in summary tables.

All summaries will include the number and percentage of subjects experiencing each type of event based on PT and the total number of each type of event, in order of overall frequency and/or SOC. Serious AEs and non-serious AEs will be summarized by PT.

Maximum level of seriousness and intensity occurring during the treatment phase for each AE will be summarized separately and by causality (probable or possible versus not related).

Considering the potential imbalance in treatment exposure, the total number of AEs and the AE rate will be calculated and summarized. The AE rate will be calculated as the total number of AEs divided by the total patient years per treatment group.

Separate listings and summary tables will be provided for all serious adverse events (SAEs), AEs leading to the discontinuation of the study drug, and all deaths during the study.

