### **12.8 DISEASE-RELATED EVENTS**

All disease-related events occurring during the study will be listed for all subjects. Overall frequency of each type of event will be summarized by treatment group.

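### Hospitalizations, hospital days and disease-related events are summarized by arm without a person-time denominator, although follow-up ends at first clinical worsening and the AE section already adds a rate per patient-year

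*SAP*

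**What the plan says.** SAP 11.2 (Resource Utilization Measures) names four quantities to be summarized by arm: "Number of hospitalizations, number of hospitalizations for PAH, total duration of hospitalization, and total duration of hospitalization for PAH". The sentence closes by saying only that "total duration of hospitalization for PAH will be summarized for each treatment group". SAP 12.8 (Disease-Related Events) says: "Overall frequency of each type of event will be summarized by treatment group". Neither section mentions a rate, patient-years or a follow-up window.

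SAP 12.2 (Adverse Events) does: "Considering the potential imbalance in treatment exposure, the total number of AEs and the AE rate will be calculated and summarized". It defines the measure: "The AE rate will be calculated as the total number of AEs divided by the total patient years per treatment group".

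Three other provisions matter:

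- Protocol 3.1 sets the main exit rule: "Subjects will continue in the study until either they experience clinical worsening as defined in the protocol". The other exits are premature discontinuation and the end of the trial at about 205 adjudicated events.
- Protocol 9.1.3 says that listed progression events which the investigator attributes to PAH "should not be recorded as AEs in the eCRF as these PAH symptoms will be evaluated" as efficacy endpoints or captured as disease-related events. Exceptions are events that are serious, possibly caused by study drug, or worse than expected.
- SAP 10.1.1.3 lists "Time to hospitalization due to worsening PAH" as a component to be analyzed in the same way as the composite endpoint.

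**The concern.** The trial is powered on the arms differing in time to clinical worsening, and clinical worsening ends participation. If the drug works as planned, UT-15C subjects are observed for longer. An arm observed for longer collects more admissions, hospital days and disease-related events at the same underlying rate. SAP 12.2 recognizes this and corrects for it with AEs; SAP 11.2 and 12.8 do not.

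The AE rate does not fill the gap. Non-serious progression events are mostly kept out of the AE data, so SAP 12.8 is their main summary by arm. Admissions that are serious AEs enter the overall AE rate, but not as a separate line, and hospital days do not enter it at all.

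What is at stake is how two descriptive tables read. Someone comparing the columns could take a follow-up difference for a difference in disease burden.

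**Working it through.** **1. The plan's own figures.** Protocol 10.2 and SAP 5 give 205 events, hazard ratio 0.62, two-sided alpha 0.05 and at least 90% power.

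- Schoenfeld: √205/2 × |ln 0.62| = 3.422; 3.422 − 1.960 = 1.462, so power is 92.8%. The claim holds.
- UT-15C median: 32/0.62 = 51.6 months (stated as 51).
- Month 12 event rates: 1 − exp(−12 ln2/32) = 22.9%, and 14.9% with the hazard multiplied by 0.62 (stated as 23% and 15%).

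The documents give no figure for hospitalizations or disease-related events.

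**2. Inputs for person-time.** Worsening hazards per month are ln2/32 = 0.02166 (placebo) and 0.62 × 0.02166 = 0.01343 (UT-15C). Accrual takes 36 months (Protocol 10.2), assumed uniform. Dropout of 10% by the end of the study is read as 10% by 48 months, the estimated duration in Protocol 3.5: −ln(0.9)/48 = 0.00220 per month in each arm.

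**3. Formula.** Let h be the worsening hazard plus the dropout hazard, and T the calendar end in months. Mean time on study for T ≥ 36 is

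(1/h) × {1 − [exp(−h(T − 36)) − exp(−hT)]/(36h)}.

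For T < 36, replace T − 36 by 0 and 36h by hT.

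**4. Worked case, N = 610, T = 43.5.**

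- Placebo, h = 0.02386: [0.8362 − 0.3543]/0.8588 = 0.561; (1 − 0.561)/0.02386 = 18.40 months.
- UT-15C, h = 0.01562: [0.8894 − 0.5068]/0.5625 = 0.680; (1 − 0.680)/0.01562 = 20.46 months (unrounded inputs).
- Event check: 305 × (0.02166 × 18.40 + 0.01343 × 20.46) = 205. This is when the planned number of events is expected.
- Patient-years: 305 × 18.40/12 = 468 and 305 × 20.46/12 = 520.

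**5. Other stopping times.**

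| Scenario | Placebo (months) | UT-15C (months) | Ratio |
|---|---|---|---|
| N = 850, about 205 events at month 35.3 | 13.58 | 14.81 | 1.09 |
| N = 610, about 205 events at month 43.5 | 18.40 | 20.46 | 1.11 |
| Month 48 | 20.79 | 23.42 | 1.13 |

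If instead 10% of randomized subjects are actually observed to drop out, the ratios are 1.09 (N = 850, 205 events at month 36.3), 1.11 (N = 610, 205 events at month 44.7) and 1.12 (month 48).

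**6. Effect on totals.** Expected total = common rate × patient-years. The rates are assumptions. With 468 and 520 patient-years, 0.1 per year gives 47 vs 52 events, 0.2 gives 94 vs 104, and 0.5 gives 234 vs 260. Dividing by patient-years returns a rate ratio of 1.00 each time.

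**7. Sensitivity at month 48.**

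- Hazard ratio 0.70 gives 1.10; 0.80 gives 1.06; 1.0 with equal dropout gives 1.00.
- At hazard ratio 0.62, with dropout as the share of randomized subjects (UT-15C vs placebo): 22% vs 14% gives 1.07; 22% vs 5% gives 1.00; 30% vs 10% gives 0.97.

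**The case against.** The case for leaving the sections alone has real content.

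- **The text does not say totals.** Under SAP 8, continuous measures default to mean, SD, median and range, and discrete ones to frequency and percentage. Per-subject means scale with follow-up just as totals do. The percentage of subjects with at least one event also rises with follow-up: at month 43.5 its ratio is about 1.11 at 0.1 events per year and 1.08 at 0.5. The size varies a little by summary; the dependence stays.
- **Part is covered.** PAH hospitalization has a time-to-event analysis (Table 14.2.1.10). Serious admissions enter the overall AE rate, and SAP 12.1 tabulates duration of exposure. This stands, and it narrows the gap to all-cause hospitalizations, hospital days and disease-related events. A reader could divide by exposure, but time on drug is not time on study.
- **Nothing is tested.** Neither section plans a test or an interval, and resource use as it occurred is a legitimate description. This is why the counts should stay.

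A reader might infer three stronger claims that the documents do not support.

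1. That subjects leave at any first hospitalization or disease-related event. They leave at first clinical worsening; among admissions for PAH or right heart failure, only non-elective stays of at least 24 hours qualify.
2. That AE discontinuation as in TDE-PH-301 (14% vs 5%, Protocol 1.2.4) would reverse the direction and flatter UT-15C. At hazard ratio 0.62, spreading that dropout over 48 months gives a ratio of about 1.06 to 1.09; placing it all in the first 16 weeks gives 1.02. Reversal needs a larger imbalance or a weaker effect.
3. That a formal treatment comparison is biased. None is planned on these measures.

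**Conclusion.** The point holds as a reporting gap. SAP 11.2 and 12.8 lack the person-time denominator that SAP 12.2 adopts for the same reason. Under the planning assumptions UT-15C accrues about 9% to 13% more person-time, so equal rates would appear as roughly that much excess in event totals on UT-15C.

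The size depends on exponential times, uniform accrual, hazard ratio 0.62 and 10% dropout in both arms. It falls to about 6% at hazard ratio 0.80 and disappears at 1 with equal dropout. Heavier discontinuation on UT-15C also reduces it and, if large enough, can reverse it. The direction in the actual data cannot be known in advance, which is a further reason to show the denominator.

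The consequence is small. The primary endpoint, alpha, sample size and testing hierarchy are untouched.

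**What to change.** In SAP 11.2 and 12.8, and in Tables 14.2.7 and 14.3.7:

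- Keep the planned counts and durations.
- Add, by arm, total patient-years and events per 100 patient-years, plus hospital days per 100 patient-years in Table 14.2.7, following SAP 12.2.
- State whether the denominator is time on study or time on drug, and match it to the window in which events are counted. SAP 12.2 says only total patient-years, in the context of treatment exposure. Protocol 7.4 encourages subjects who stop drug before Week 24 to stay until Week 24, so the two denominators differ.
- Add a note that a qualifying PAH hospitalization (non-elective, at least 24 hours) normally ends participation, so the PAH count is close to a first-event count.

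No rate ratio or confidence interval is needed. SAP 12.2 plans none for AEs, and for clustered hospital days one would require a variance model.

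The cost is SAP wording, one decision on the denominator, and added columns in two descriptive tables. No new data are needed.

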## 12 SAFETY ANALYSES

All safety analyses will be performed only on the Safety Population (see Section 6).

### 12.1 EXTENT OF EXPOSURE

All study drug dosing will be listed for all subjects. The listing will include initial dose and date of this initial dose, dose and date of each change, and whether each change applied to the morning, afternoon, or evening doses. Dosing at Weeks 4, 8, 12, 24, and every 12-week follow-up assessment will be summarized for subjects still receiving study drug at each of these assessments. A summary by treatment group of maximum study drug dose and overall duration of exposure will be included. The study drug dosing and exposure by the use of background PAH therapy will be provided in a separate summary.

In addition, a summary table will be provided for study drug treatment compliance for the first 24 weeks by treatment group. The summary will include the number and percent of days subjects are dosed and total study drug consumed for first 24 weeks.

### 12.2 ADVERSE EVENTS

All AEs will be coded using MedDRA and will be listed by treatment group, including all the details on the eCRF page plus an indicator of whether the event was treatment emergent. The AE listings will include the AE verbatim term and its corresponding PT and SOC.

The AE summary tables will be limited to include only treatment-emergent AEs and will be summarized for each treatment group. Treatment-emergent AEs are those AEs with an onset date equal to or after the start date of the study drug. The non-treatment emergent AEs (the AEs that occur after signing the informed consent form, but before receiving study drug, will be listed but will not be included in summary tables.

All summaries will include the number and percentage of subjects experiencing each type of event based on PT and the total number of each type of event, in order of overall frequency and/or SOC. Serious AEs and non-serious AEs will be summarized by PT.

Maximum level of seriousness and intensity occurring during the treatment phase for each AE will be summarized separately and by causality (probable or possible versus not related).

Considering the potential imbalance in treatment exposure, the total number of AEs and the AE rate will be calculated and summarized. The AE rate will be calculated as the total number of AEs divided by the total patient years per treatment group.

Separate listings and summary tables will be provided for all serious adverse events (SAEs), AEs leading to the discontinuation of the study drug, and all deaths during the study.

